COVER PAGE

TITLE:

Efficacy and safety of low dose Amisulpride Versus Olanzapine-Fluoxetine Combination in the treatment of Post Schizophrenic Depression: A Randomised Controlled Trial

NCT04876521

DATE: June 1, 2019

STUDY PROTOCOL, STATISTICAL ANALYSIS PLAN & INFORMED CONSENT FORM

STUDY PROTOCOL

FULL TITLE:

Efficacy and safety of low dose Amisulpride Versus Olanzapine-Fluoxetine Combination in the treatment of Post Schizophrenic Depression: A Randomised Controlled Trial

BRIEF TITLE:

Low Dose Amisulpride Vs Olanzapine-Fluoxetine Combination in Post-Schizophrenic Depression (PSD-AOFC)

SCIENTIFIC BACKGROUND:

About one-fourth of patients who have schizophrenia ultimately develop post-schizophrenic depression (PSD) with higher morbidity and mortality risks, including a higher number of suicides (1-2). Studies regarding the pharmacological treatment options for PSD are scarce. Very few clinical trials have been conducted with antipsychotics involving small study samples (3-4). Moreover, antipsychotics are Serotonin-Dopamine Antagonists, an action opposite to that of antidepressants (5), so their exact role in treating PSD needs further exploration. Antidepressants have been used in schizophrenia with depression but have shown little success (6). An antipsychotic along with an antidepressant (like an olanzapine-fluoxetine combination, OFC) is now the commonly practised treatment strategy in PSD. However, there is insufficient evidence in the literature confirming its rationality.

Studies have shown that amisulpride in a lower dose range (50-400 mg/day) has shown antidepressant actions (7). However, amisulpride has never been explored in PSD. Amisulpride monotherapy might have the added advantage of avoiding polypharmacy in these patients.

Also, correlating the clinical findings with changes in serum Brain-Derived Neurotrophic Factor (BDNF), a neuro-biomarker constantly studied in depressive conditions, would help substantiate the results (8). In our present study on PSD, we would like to corroborate the efficacy of the interventions (low-dose amisulpride versus OFC) with the changes in serum levels of BDNF.

NULL HYPOTHESIS:

There is no difference in the change in the Calgary Depression Scale for Schizophrenia (CDSS) scores between the study groups over 8 weeks.

ALTERNATE HYPOTHESIS:

There is a difference in the change in the Calgary Depression Scale for Schizophrenia (CDSS) scores between the study groups over 8 weeks.

AIM:

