All patients under the study will be followed for a period of 8 weeks from the start of the intervention. Then, the follow-up assessments will be done by rating the CDSS, and the CGI scales once again in each patient. Serum BDNF levels will be tested again. The data obtained will be compared within each group to find the change before and after the respective interventions. Thereafter, the magnitude of the changes will be compared in-between the groups to find out the efficacy and safety of one treatment over the other. All the results will be statistically tested to understand their significance.

OUTCOME MEASURES:**Primary Outcome Measure:**

1. Calgary Depression Scale for Schizophrenia (CDSS) [Time Frame: 8 weeks]

Calgary Depression Scale for Schizophrenia (CDSS) (13) scores will be used to measure the change in the severity of depressive symptoms in the study groups from baseline over 8 weeks. the total score ranges from 0 - 36. Higher scores represent higher severity of depression.

Secondary Outcome Measures:

1. Clinical Global Impression (CGI) [Time Frame: 8 weeks]

Clinical Global Impression (CGI) scores (14) will be used to measure the change in illness severity, global functioning and improvement in the study groups from baseline over 8 weeks.

- The Clinical Global Impression - Severity scale (CGI-S) is a 7-point scale [minimum: 1 and maximum 7]: Higher scores means higher severity of disease.
- The Clinical Global Impression - Improvement scale (CGI-I) is a 7 point scale [minimum: 1 and maximum 7]: Higher scores means more clinical improvement.

2. Serum BDNF Levels [Time Frame: 8 weeks]

The change in serum BDNF levels in the study groups over 8 weeks.

3. Correlation [Time Frame: 8 week]

Determine the correlation (if any) between the between changes in CDSS scores, CGI scores and serum BDNF levels

4. Adverse Drug Reactions [Time Frame: 8 weeks]
Detect adverse drug reactions (if any) and grading their severity

STATISTICAL ANALYSIS PLAN:

1. The CDSS scores, the CGI scores and the serum levels of BDNF, being continuous variables would be expressed as a mean \pm standard deviation (SD) / standard error of means (SEM)
2. The means would be compared within the group by two-sided paired t-test / Wilcoxon signed rank test
3. The means between the groups would be compared using unpaired t-test / Mann Whitney U test
4. Correlation analysis will be done between the CDSS ratings, the CGI scores and the serum BDNF levels.

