5. The missing values would be replaced by the help of multiple imputations for conducting an Intention to Treat (ITT) analysis and the pooled data would be used for further analysis
6. All the statistical analyses would be performed using SPSS 23.0 (IBM, NY USA)
7. For obtaining statistically significant results, P value would be set at < 0.05

SAMPLE SIZE CALCULATION:

A sample size of 26 per group will achieve a power of 80%, to detect a difference of 3 in Calgary Depression Scale for Schizophrenia (CDSS) between the groups with known SD of 3.8 and with a significant level 0.05 using a Two-sided Two-sample T-test. Assuming attrition of 10-15% 30 patients in each group will be recruited.

Sample size calculation was done by PASS software (Version 11)

EXPECTED OUTCOME:

- The role of low dose Amisulpride in the treatment of Post Schizophrenic Depression can be explored for the first time (as no study has been done on it yet)
- Low dose Amisulpride is expected to be more efficacious than Olanzapine-Fluoxetine combinations in PSD. If this comes true, a new treatment strategy in PSD would be obtained.
- Use of Amisulpride in PSD would have the following advantages:
 1. Polypharmacy in PSD patients can be avoided
 2. Overall reduction in the medical expenditure of the patients
 3. Duration of treatment would not be an issue as in the case of treatments with antidepressants
 4. In advent of positive symptoms simply hiking the Amisulpride doses to higher dose range can treat the patients, without switching to any other antipsychotic.
 5. Lesser risk of side-effects in the patients, as Amisulpride is a relatively safer drug among other antipsychotics

ETHICAL ISSUES:

1. All works under the proposed study would begin only after obtaining approval from the Institutional Ethics Committee, AIIMS Bhubaneswar
2. All the patients and their family members/ guardians would be adequately explained, in the language they understand, about the study procedure and the possible risks and benefits associated with it. Only those patients with a written Informed Consent from the Legally Authorised Relative would be enrolled for the study.
3. Strict confidentiality would be maintained about the identity, sensitive information and personal details of the patients obtained during the course of the study.
4. Any patient can willfully withdraw his/ her participation at any point during the course of the study.

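### The primary CDSS test is left as t-test or Mann-Whitney, and the multiple imputation in item 5 has no stated pooling that the rank branch could use

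*Combined protocol and SAP*

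**What the plan says.** All places are in the combined protocol and SAP.

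- **Hypothesis (Null Hypothesis).** "There is no difference in the change in the Calgary Depression Scale for Schizophrenia (CDSS) scores between the study groups over 8 weeks".
- **Summary scale (SAP item 1).** CDSS, CGI and BDNF, "being continuous variables would be expressed as a mean", are given with SD or SEM.
- **Between-group test (SAP item 3).** "The means between the groups would be compared using unpaired t-test / Mann Whitney U test". This is the only between-group test in the plan, so it covers the primary outcome. No normality criterion, decision rule or ranking of the two tests appears anywhere.
- **Missing data (SAP item 5).** "The missing values would be replaced by the help of multiple imputations for conducting an Intention to Treat (ITT) analysis". The item adds that the data, once pooled, feed the later analyses. It gives no number of imputations, imputation model, quantity to be pooled or pooling rule.
- **Significance (SAP item 7).** "For obtaining statistically significant results, P value would be set at < 0.05".
- **Sizing (Sample Size Calculation).** 26 per group for a 3-point CDSS difference, SD 3.8, "with a significant level 0.05 using a Two-sided Two-sample T-test". With 10-15% attrition expected, 30 per group are recruited.

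Item 2 has the same construction for within-group tests ("The means would be compared within the group by two-sided paired t-test / Wilcoxon signed rank test"), but those are not the primary comparison.

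**The concern.** Items 3 and 5 do not fit together on one of the two branches. Rubin's rules take an estimate and its standard error from each imputed set. A t-test supplies both: the mean difference and its standard error. The Mann-Whitney test as the plan names it supplies neither. An analyst on that branch would have to improvise, for example by testing one completed set, testing a data set of averaged imputations, or picking among several P values. The first two treat imputed values as if they had been observed.

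The two tests also need not answer the same question. The trial is sized on a mean difference and item 3 speaks of means, whereas Mann-Whitney addresses the mean difference only when the arms differ by a pure shift.

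Finally, with no rule, the reported primary P value depends on a choice that the plan does not fix. At stake are the error rate and the interpretation of the one confirmatory result.

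**Working it through.** **1. The plan's own sample size.** n = 2[σ(z₀.₉₇₅ + z₀.₈₀)/δ]² = 2[3.8 × (1.960 + 0.842)/3]² = 25.19, rounded up to 26. This reproduces the plan's figure. Power at 26 is 81.2% with the SD known and 79.7% by the noncentral t; at 30 the latter is 85.2%. The sizing therefore belongs to a test of means.

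**2. What pooling needs.** With estimates q₁…qₘ and average within-set variance W, Rubin's rules give q̄ and T = W + (1 + 1/m)B, where B is the variance of the qⱼ. For m = 5, T = W + 1.2B. The t-test branch supplies q and its variance. The Mann-Whitney branch supplies Uⱼ and Pⱼ, and T cannot be formed from them.

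**3. Effect of testing imputed data without that pooling.** Attrition of 10-15% of 30 is 3 to 4.5, so 3-5 missing per arm were simulated. Assumptions: no true difference, missing at random, 5 imputations, imputation model with arm and baseline, 8,000 trials per row. Monte Carlo standard error near 5% is √(0.05 × 0.95/8,000), about 0.24 points.

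| Missing per arm | Rubin-pooled mean difference | Mann-Whitney, one completed set | Mann-Whitney, averaged imputations | t-test, averaged imputations | Five Mann-Whitney P values on both sides of 0.05 |
|---|---|---|---|---|---|
| 3 | 4.8% | 7.0% | 7.3% | 7.0% | 8.7% |
| 4 | 5.2% | 7.7% | 8.5% | 8.2% | 11.4% |
| 5 | 4.9% | 8.7% | 9.7% | 8.8% | 14.3% |

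A separate simulation of the same design gave 4.9-5.3%, 6.8-8.3%, 7.1-9.1%, 7.1-9.4% and 9-14% for the same five columns.

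**4. Effect of the open choice alone.** Complete data, 26-30 per arm, SD 3.8, same distribution in both arms, 100,000 trials per scenario:

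- t-test alone: 4.5-5.1%. Mann-Whitney alone: 4.9-5.1%.
- Smaller of the two P values: 5.9-6.1% for normal data, 6.3-6.7% for skewed or heavy-tailed rounded scores.
- Choice by a Shapiro-Wilk check (8,000 trials, 30 per arm): 5.0-5.2%.
- With a true 3-point difference and normal data, the tests disagree on significance in 5.4% of trials at 26 per arm and 4.4% at 30.

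**5. Whether the rank test targets the mean.** With equal means and SDs, one arm skewed and the other normal, Mann-Whitney rejects in 6.5-8.3% of trials and the t-test in 5.0-5.3%.

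**6. Power given up by fixing the t-test.** True 3-point shift, 26 per arm:

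- Normal data: t-test 79.7%, Mann-Whitney 77.2%.
- Gamma shape 2 in both arms: 79.3% against 88.8%, a loss of 9.5 points.
- Gamma shape 1.5 in both arms: 80.0% against 90.9%, a loss of 10.9 points.

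Across the runs made, the loss under skew was about 8-11 points. All shapes are assumptions; the documents give no distribution for CDSS change.

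**The case against.** The other side has several good points.

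- **The slash may be innocent.** Item 3 serves CDSS, the CGI scales and BDNF together, so it may mean a test suited to each variable. The only test named specifically for CDSS is the two-sample t-test of the sizing paragraph. That makes the t-test the likelier intention, but a sizing sentence does not bind the analysis.
- **A normality check is the usual reading of such a slash.** When the arms share a shape, it holds about 5%. This stands. In a skewed-against-normal case with equal means the same rule gave 7.0%, and the plan states no such rule in any case.
- **Rank methods can be pooled.** A Hodges-Lehmann shift, or the probability that one arm exceeds the other, with a standard error, could go through Rubin's rules. This is correct, and it limits the point to the test as named. The plan mentions neither.
- **Item 5 is at fault for both tests.** Averaged imputations inflate the t-test to 7.0-8.8% in the table above, so deleting the slash alone would not cure the problem. This stands, and the fix covers item 5.

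A reader might infer that the primary type I error is already something other than 0.05, or that someone will report whichever P is smaller. The documents support neither. No passage proposes computing both tests, and the excess arises only if the test is picked by its result or if imputed data are tested without valid pooling. Nor should much weight rest on extreme shapes. Mirror-image skew in the two arms gives Mann-Whitney 13.4%, but nothing in the documents suggests that pattern, and the null hypothesis as worded does not mention means.

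**Conclusion.** The point holds in limited form. The plan names no single primary test, and one of its two candidates has no defined result under the intention-to-treat analysis that item 5 promises.

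The larger numerical effect comes from imputation: about 7-9% error (9.7% at the extreme of one run) if one completed or averaged set is tested, against about 5% for the Rubin-pooled mean difference. This assumes 3-5 of 30 missing per arm at random and 5 imputations. The effect of test choice alone is modest: about 6% if the smaller P is taken from normal data, up to 6.7% with skewed or heavy-tailed scores, and about 5% under a normality-based choice with a common shape. The mismatch between ranks and means matters only if the arms differ in shape as well as location.

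The error rate is therefore not guaranteed at 0.05; it is not shown to be broken. The sample size is unaffected.

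**What to change.** Make these changes before outcome data are examined by arm. Only the rater is stated to be blinded, so an unblinding date would not be a usable milestone.

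1. **Item 3.** Name one primary analysis: the two-sided comparison of mean CDSS change at 0.05, either as the unpaired t-test on which the trial is sized or as its baseline-adjusted form. Write down one of the two.
2. **Item 5.** Replace the statement that pooled data are carried forward. Say that each imputed set is analysed separately and that the mean difference and its standard error are combined by Rubin's rules. State the number of imputations and the imputation model.
3. **Mann-Whitney.** Keep it as a supportive analysis of observed data that cannot replace the primary result.

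The cost is a few sentences and no extra patients: t-test power stays at 79.7% with 26 per group and 85.2% with 30. The real downside is the loss of about 8-11 points of power against the rank test if CDSS change is strongly skewed in both arms (about 80% against 89-91% at 26 per arm under the assumed gamma shapes). With normal data the t-test gains about 2 points.

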To compare the efficacy and safety of low dose Amisulpride Versus Olanzapine-Fluoxetine Combination and in patients with Post Schizophrenic Depression.

STUDY OBJECTIVES:**PRIMARY OBJECTIVES:**

1. To evaluate the change in the severity of depression in terms of change in Calgary Depression Scale for Schizophrenia (CDSS) scores in the study groups over 8 weeks

SECONDARY OBJECTIVES:

1. To evaluate the change in symptom severity and improvement in terms of change in Clinical Global Impression (CGI) scores in the study groups over 8 weeks
2. To evaluate the change in serum BDNF levels in the study groups over 8 weeks
3. To determine the correlation (if any) between the changes in CDSS scores, CGI scores and serum BDNF levels
4. To detect adverse drug reactions (if any) and grading their severity

MATERIALS AND METHODS**STUDY SETTING:**

The proposed study will be conducted at the Out-Patient (OP) and the In-Patient (IP) settings of the Department of Psychiatry, All India Institute of Medical Sciences, Bhubaneshwar.

STUDY DESIGN:

The proposed study will be a randomized, rater-blinded, controlled, clinical trial

STUDY PERIOD:

The study will be conducted within the time frame of two years.

STUDY POPULATION:

The proposed study will be conducted on the patients diagnosed with Post Schizophrenic Depression of the catchment area pertaining to AIIMS, Bhubaneswar.

INCLUSION CRITERIA:

All patients coming for treatment at the OPD and IPD of the Department of Psychiatry fulfilling the following are included:

1. Patients with Post Schizophrenic Depression according to ICD10-DCR (International Classification of Diseases 10– Diagnostic Criteria for Research) (9).
2. Aged between 18 to 60 years of either sex
3. Patients with a positive score of less than 29 on the Positive and Negative Syndrome Scale (PANSS) (10)
4. Patients with a score of more than 6 on the Montgomery-Asberg Depression Rating Scale (MADRS) (11)
5. Patients without Extrapyramidal symptoms: a score of less than 3 on the Simpson-Angus Scale (12)
6. With Informed consent from the Legally Authorised Relative

EXCLUSION CRITERIA:

Patients with any one of the following are excluded from the study:

1. Patients with a medical or neurological disorder
2. Patients with a history of substance dependence
3. Patients with high suicidality
4. Patients with a past history of primary depression
5. Patients already on Olanzapine-Fluoxetine combination or Amisulpride

METHODOLOGY:

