The proposed study would be an 8-week, randomised, controlled, parallel-group, clinical trial which will be conducted at the Inpatient and Outpatient settings of the Department of Psychiatry, AIIMS, Bhubaneswar. Patients with the diagnosis of Post Schizophrenic Depression according to the ICD 10 (DCR) and meeting all the Inclusion and Exclusion Criteria would be selected for the study. At first, the patients and their family members/ guardians would be explained about the study procedure along with its possible risks and benefits using a Patient Information Sheet (in their local language). After obtaining a written Informed Consent from the Legally Authorised Relative, the patients would be finally recruited for the study.

All recruited patients would be randomized using computer-generated random numbers into two treatment groups with an allocation ratio of 1:1. The sociodemographic and clinical data of the patients would be collected as per the designed sheets. Then at baseline, the CDSS and CGI ratings would be assessed, and the serum BDNF would be tested for each patient. The study would be rater-blinded. The experimental group would receive Amisulpride at a low dosage of 100-300 mg/day and the control group would receive a combination of Olanzapine at 5mg or 10 mg/day and Fluoxetine at 20mg/day.

The two groups would be followed for 8 weeks, at the completion of which all the patients would be reassessed. The follow-up assessment would involve a re-evaluation of the CDSS and the CGI scores and the Serum BDNF levels to see for any change. The data thus collected would be analysed, compared within and in between the study groups and statistical tests would be applied for drawing conclusions.

RANDOMIZATION:

All recruited patients will be randomized by computer-generated random number into two treatment groups with an allocation ratio of 1:1.

BLINDING:

The proposed study will be rater-blinded. The ratings of the CDSS and CGI scales would be done by a psychiatrist who would be blinded to the nature of the intervention provided.

FOLLOW UP:

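### The SAP does not say whether the CDSS-CGI-BDNF correlation is overall, within arm or adjusted for arm; if arm is ignored, arm differences in both changes can create or hide a correlation.

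*Combined protocol and SAP*

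**What the plan says.** The analysis is described in three places, none of which mentions treatment arm.

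- Statistical Analysis Plan, item 4: "Correlation analysis will be done between the CDSS ratings, the CGI scores and the serum BDNF levels".
- Secondary Objectives, item 3: "To determine the correlation (if any) between the changes in CDSS scores, CGI scores and serum BDNF levels".
- Outcome Measures, secondary outcome 3, which repeats the objective.

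No coefficient is named. Item 4 speaks of ratings, scores and levels, while the objective speaks of changes.

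The Scientific Background gives the purpose of the BDNF measurements: the investigators want to "corroborate the efficacy of the interventions (low-dose amisulpride versus OFC) with the changes in serum levels of BDNF".

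Nearby text does refer to the groups. SAP items 2 and 3 specify within-group and between-group comparisons of means, and the BDNF objective reads "To evaluate the change in serum BDNF levels in the study groups over 8 weeks". The Methodology says of the data in general that they will be "compared within and in between the study groups and statistical tests would be applied for drawing conclusions".

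**The concern.** A simple correlation over both arms mixes two things: whether patients whose BDNF changes more also improve more, and whether one arm has larger mean changes in both variables. Only the first shows that BDNF tracks clinical response. The second can arise when BDNF and mood are unrelated inside each regimen.

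Half of the condition is built into the design. The trial is sized to detect a CDSS difference between arms, and the Expected Outcome section anticipates that amisulpride will do better. If BDNF change also differs between the two regimens, an unadjusted coefficient may be read as BDNF corroborating efficacy when it partly restates the treatment difference. If the arm shifts run against the within-arm relation, a real association may be missed. Because the text leaves the choice open, it could also be made after the results are seen.

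**Working it through.** **Inputs from the documents.** The Sample Size Calculation gives a CDSS difference of 3, SD 3.8, two-sided 5% level, 80% power, 26 per group, and 30 per group recruited for 10-15% attrition. Allocation is 1:1. The SAP sets significance at P < 0.05.

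**Assumptions.** The 3 and 3.8 are taken as the difference and SD of the CDSS change; the protocol does not say which SD 3.8 is. The documents give no BDNF difference or SD, so the standardised BDNF difference is varied from 0 to 1.0. Changes are normal within arm, and the test is Pearson's.

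**The plan's own figure.** n per group = 2 × (1.96 + 0.84)² × 3.8² / 3², which is about 25.2, so 26. Power at 26 per group from the noncentral t is 79.7%, which agrees with the stated 80%. For attrition, 26/0.90 = 28.9 and 26/0.85 = 30.6, so 30 lies in the range. The sample size reproduces. The documents give no figure for the correlation.

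**Overall correlation when arm is ignored.** Let d1 and d2 be the arm differences in CDSS and BDNF change, in within-arm SDs. With equal arms and zero within-arm correlation, the covariance over all patients is d1·d2/4 and the variances are 1 + d1²/4 and 1 + d2²/4. Hence

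r = (d1·d2/4) / √[(1 + d1²/4)(1 + d2²/4)].

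Here d1 = 3/3.8 = 0.789 and d1²/4 = 0.156. For d2 = 0.789, r = 0.156/1.156 = 0.13. For d2 = 1.0, r = 0.197/√(1.156 × 1.25) = 0.16.

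**False-positive rates.** These come from simulation (40,000 or more trials per setting) at the nominal two-sided 5% level.

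| BDNF difference (SD, assumed) | r ignoring arm | Rejects, 30 per arm | Rejects, 26 per arm | Rejects, adjusted for arm |
|---|---|---|---|---|
| 0 | 0.00 | 5% | 5% | 5% |
| 0.2 | 0.04 | 6% | 6% | 5% |
| 0.5 | 0.09 | 10% | 10% | 5% |
| 0.79 | 0.13 | 18% | 16% | 5% |
| 1.0 | 0.16 | 24% | 22% | 5% |

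The r values are absolute; the sign depends on the direction of the two shifts. If d1 is 0, r is 0 and the rate is 5% whatever d2 is. The critical |r| is 0.25 for 60 patients and 0.27 for 52, so every induced r in the table lies below the threshold. The effect is a raised error rate, not usual significance.

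**Masking.** Assume a within-arm correlation of -0.4, with arm shifts opposing it. The numerator becomes -0.4 + d1·d2/4. For d2 = 0.79 the overall r is (-0.4 + 0.156)/1.156 = -0.21. In simulation at 30 per arm, the chance of detecting the correlation is about 89% when adjusted for arm. When arm is ignored it is about 56%, 35% and 23% for BDNF differences of 0.5, 0.79 and 1.0 SD.

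**The case against.** A reader might infer that the plan commits to one correlation over all patients regardless of arm, because item 4 and objective 3 omit the groups while their neighbours name them. The documents do not support that. SAP item 1, on summary statistics, also names no group, yet items 2 and 3 compare those means within and between groups. Objective 4, on adverse reactions, names none either, yet the Follow Up section compares safety between treatments. The Methodology sentence quoted above is not specific to the correlation, but it leans away from ignoring arm. In item 5, "the pooled data would be used for further analysis" follows the multiple-imputation clause and does not describe combining arms. The text is silent, and a within-arm analysis fits it too.

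Three further objections deserve an answer.

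- The harm needs an arm difference in BDNF change, and the documents state neither a size nor a direction. This stands: with none, there is no distortion.
- The induced r is modest. This also stands. A reader should not infer that an unadjusted coefficient would usually be significant for this reason alone.
- Since the stated aim is to corroborate efficacy, whether the better arm also shows more BDNF change may be part of the question, and adjusting for arm discards it. This does not stand. SAP item 3 already compares BDNF between the arms, so what the correlation adds is patient-level tracking, and that is the part arm differences contaminate.

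**Conclusion.** The point holds as a gap in specification. No section plans a within-arm or arm-adjusted correlation, and a simple correlation run literally from item 4 can mislead in the situation the trial is sized for, if BDNF also differs by arm. The inflation is negligible for a small BDNF difference and reaches roughly one false positive in four or five at 1.0 SD. These sizes rest on reading 3.8 as the SD of change, on zero within-arm correlation, and on BDNF differences that are assumed. They were worked for CDSS with BDNF; the same algebra applies to CGI, but the documents give no CGI difference to put in.

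Severity is low. This is a secondary analysis, and neither the primary CDSS comparison nor the sample size is affected.

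**What to change.** Extend SAP item 4 along these lines: the overall coefficient will be the partial correlation of the baseline-to-week-8 change scores adjusted for treatment arm; within-arm coefficients will be shown descriptively; the adjusted coefficient alone will be used to judge whether BDNF tracks clinical change. Name the coefficient, and bring item 4 into line with objective 3 by referring to changes. Leave the question of whether the arms differ in BDNF to item 3.

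The cost is one sentence and one degree of freedom. No new data are needed, and SPSS, already the planned software, computes partial correlations. The per-arm coefficients will be imprecise: with 30 patients an |r| of about 0.36 is needed for significance, and with 26 about 0.39, which is why they should be descriptive only.
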